6.4 Point of Registration

Lead-In subjects will be considered registered in the trial upon calling IVRS.

During the randomization phase, the subject is considered randomized after IVRS has been called and a device has been assigned (Absorb BVS or XIENCE). The subject is considered registered and in the ITT population at the point of randomization. Once randomization is completed and a treatment arm is assigned, crossover is not permitted.

Registered subjects count toward the total sample size in ABSORB III. Refer to **Appendix IV** and **Figures 1 and 2** for further registration details.

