 - The expanded diameter of the post dilatation balloon must be within the allowable expansion limits of the scaffold. Do not dilate the Absorb BVS beyond the dilatation limit which is 0.5 mm above the nominal diameter. Doing so may result in scaffold damage. Thus, it is highly recommended that the compliance chart of the non-compliant balloon selected must be carefully reviewed prior to dilatation and an appropriate maximum pressure used to ensure that the scaffold is not over-dilated.

Table 3.0 Scaffold Diameter and Maximum Diameter Limit

Nominal Scaffold Diameter	Post Dilatation Maximum Diameter Limit
2.5 mm	3.0 mm
3.0 mm	3.5 mm
3.5 mm	4.0 mm

- The delivery balloon cannot be removed from the body and reinserted and used for post-dilatation
- IVUS or OCT guidance may be used as per standard of care.
- Please refer to the physician training deck for user guidance in handling procedural issues (e.g., difficult in recrossing an implanted scaffold for purposes such as intravascular imaging or post-dilatation if needed).

Imaging Cohort

If subject is in the Imaging Group (See **Appendix VI and Imaging Guidance Document** for further details):

- Post-procedure angiography, IVUS and OCT are required based on respective imaging groups.
- If post-dilatation was performed, post-procedure imaging must be conducted following last balloon inflation.

If two target lesions are treated, post-procedure imaging must be done on the first target lesion after its successful treatment, and then after successful treatment of the 2nd target lesion.

7.3.5 *Bailout Stenting or Alternative Procedures*

Bailout procedures may be performed if the subject experiences:

- Dissection requiring intervention
- Occlusive complication as evidenced by a decrease in target vessel flow
- Chest pain or ischemic changes measured by ECG that do not respond to repeat balloon inflations, medical therapy or lytic agents
- Unplanned additional device is required to cover the target lesion

In the randomized subjects, if a bailout device is required for a target lesion (e.g., for edge dissection), the same device as the implanted device must be used. Overlap of the bailout stent/scaffold with the implanted stent/scaffold should be 1-2 mm. Gaps should be avoided.

- Use Absorb BVS if target lesion is treated with Absorb BVS.
- Use XIENCE if target lesion is treated with XIENCE.

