- If a bailout with an Absorb BVS device cannot be delivered to the site of the lesion, the device should be carefully withdrawn and a XIENCE used.
- If an appropriate size Absorb BVS is not available XIENCE can be used.

If during the Lead-In phase a bailout is required, the investigator should use an appropriately sized XIENCE stent and not an Absorb BVS.

The Imaging Cohort subjects that receive metallic stent bailout of an Absorb BVS treated lesion will be required to complete imaging follow-up at the protocol specified time points of 3 years for IVUS or OCT, depending on which imaging group the subject is in. However, the subject's imaging data will not be included in the imaging study analysis and will not be counted towards the associated powered secondary endpoints analysis. These subjects may be replaced by another subject that received an Absorb BVS without metallic stent overlap.

IMPORTANT: It is required that the bailout device be placed so that there is no visible gap between the Absorb BVS and the bailout device. In such a case, at least 1 mm (minimum) to 2 mm (maximum) overlap is required.

IMPORTANT: In the rare event of acute occlusion following Absorb BVS placement, the bailout device should be XIENCE and deployed within the Absorb BVS such that the Absorb BVS is completely covered by the bailout device if this is believed to be in the best interest of the patient.

Although a bailout procedure is not considered a major adverse cardiac event (MACE) unless the subject sustains death, emergent CABG, PCI or MI, such procedures should be avoided unless required for safe subject management.

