7.3.8 Imaging Assessment

Subjects from the Imaging Cohort will receive angiography (includes vasomotion assessment), IVUS and OCT at pre-specified time-points (**Section 7.5**). Imaging assessments should be conducted per core lab guidelines in the Imaging Guidance Document distributed to each site. Intracoronary nitroglycerine should be given before all imaging runs to avoid spasm and afford maximal luminal dimensions.

Any Imaging Cohort subject that did not receive the assigned Absorb BVS or XIENCE stent will not receive follow-up imaging procedures. These subjects will be clinically followed under the study. If an Imaging Cohort subject had a TLR prior to the imaging follow-up, the imaging data at the time of TLR and at the protocol specified later imaging time points will be analyzed but not included in the imaging endpoint analysis. If an Imaging Cohort subject had a TVR or angiogram prior to the imaging follow-up, the subject will continue to have the protocol specified imaging follow-up and will not be replaced. If an Imaging Cohort subject has two target lesions but only one target lesion was successfully treated with the assigned device, the unsuccessfully treated target lesion must be imaged post-treatment and at the specified follow-up

times only if the assigned study device was implanted for lesion treatment. Imaging Cohort subjects that receive metallic stent bailout of an Absorb BVS treated lesion will be required to complete imaging follow-up at the protocol specified time points of 3 years for IVUS or OCT, depending on which imaging group the subject is in. However, the subject's imaging data will not be included in the imaging study analysis and will not be counted the associated powered secondary endpoints. These subjects may be replaced by another subject that received an Absorb BVS without metallic stent overlap.

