7.3.8.2 IVUS Pull-back of Target Vessel

- IVUS pullback (20 MHz or 40-45 MHz catheter can be used) is required post-procedure and at 3-year follow-up for the imaging study subjects.
- Pullback of the IVUS catheter should be performed from the distal reference to the guiding catheter, per IVUS core laboratory guidelines.
- If IVUS reveals any findings such that additional PCI is performed, an additional IVUS run must be performed after the last intervention.
- **Caution:** It is important to place the IVUS transducer in the center of the lumen to avoid lifting or disturbing the device struts during pullback.

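### ABSORB III's powered IVUS lumen-area test is assigned to ITT and PTE, yet Absorb subjects with a metallic bailout stent are left out of it and may be replaced

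*Protocol*

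**What the plan says.** All references are to the ABSORB III part of the protocol unless stated.

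- **Population.** Section 10.4.2 names ITT and PTE for the two-sample t-tests of both powered imaging endpoints. The Protocol Summary makes ITT the primary population. Section 6.4 states: "The subject is considered registered and in the ITT population at the point of randomization". Appendix II defines ITT the same way. Sections 10.2.1 and 10.2.2 are blacked out.
- **Metallic bailout.** Section 7.3.8 says "Imaging Cohort subjects that receive metallic stent bailout of an Absorb BVS treated lesion will be required to complete imaging follow-up" at 3 years, but that the subject's "imaging data will not be included in the imaging study analysis and will not be counted the associated powered secondary endpoints". Section 7.3.5 has the same rule. Both add: "These subjects may be replaced by another subject that received an Absorb BVS without metallic stent overlap".
- **Measurements.** Under 7.3.8.2, IVUS pullback "is required post-procedure and at 3-year follow-up for the imaging study subjects". If IVUS findings lead to more PCI, "an additional IVUS run must be performed after the last intervention".
- **Bailout device.** Section 7.3.5 calls for the device already implanted: Absorb for an Absorb lesion, and for the control arm "Use XIENCE if target lesion is treated with XIENCE". It provides for XIENCE in an Absorb lesion in three situations: the Absorb bailout device cannot be delivered, no suitable Absorb size is available, or there is acute occlusion.
- **Use of the result.** The Protocol Summary says the imaging endpoints are to support superiority label claims, one of them on late lumen enlargement. Section 10.3.2 sets a two-sided alpha of 0.05 and pools with ABSORB Japan.

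**The concern.** An ITT comparison keeps subjects in their randomised arm whatever happens afterwards. Here the ground for removal arises during the procedure, after randomisation, and bailout can create it only in the Absorb arm. Two of the three routes to it are a delivery failure and an acute occlusion, so the removed subjects need not resemble those who stay. The replacement is also chosen on something that happened after randomisation in that arm.

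At stake is whether a superiority claim on late lumen enlargement rests on a randomised comparison or on a selected Absorb group set against a XIENCE group with no matching selection.

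**Working it through.** **1. Who is kept under the visible rules (7.3.5 and 7.3.8)**

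| Situation | Arm affected | 3-year imaging | In powered IVUS test | Replacement |
|---|---|---|---|---|
| XIENCE bailed out with XIENCE | XIENCE | required | yes | no rule |
| Absorb bailed out with Absorb | Absorb | required | yes | no rule |
| Absorb bailed out with XIENCE | Absorb only | required | no | allowed |
| TLR before follow-up | both | done | no | no rule in these sections |
| Assigned device not received | both | not done | no data | no rule in these sections |
| TVR or angiogram before follow-up | both | required | yes | not replaced |

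Only the third row removes subjects from a single arm while requiring their measurement. It makes no distinction between ITT and PTE, so it reaches the analysis called ITT.

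**2. Are the data available?** For IVUS-group subjects, 7.3.8.2 requires both runs and 7.3.8 repeats the 3-year requirement for bailout subjects. The lumen-area endpoint needs nothing else. This does not carry over to vasomotion, because 7.3.8.4 says not to assess it when an Absorb lesion has metallic overlap, or to OCT-group subjects, who do not feed the IVUS endpoint.

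**3. Scale.** The plan gives no figure to reproduce: the pooled N is blacked out and no bailout rate is stated.

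- ABSORB III IVUS group (Protocol Summary): about 150 at 2:1, so 150 × 2/3 = 100 Absorb and 50 XIENCE. One Absorb subject is 1/100 = 1% of the arm; the share in the pooled Absorb arm is smaller.
- Let b be the excluded fraction, m their mean lumen-area change and A the mean change in the other Absorb subjects. The full-arm mean is (1 − b)A + bm, so leaving the group out shifts the mean by A − [(1 − b)A + bm] = b(A − m). A replacement with expected change A gives the same expected shift.
- Cohort B values for A (section 2.1.9): 6.85 − 6.53 = +0.32 mm² at 2 years (Table 2.3, p=0.3515) and 6.37 − 6.60 = −0.23 mm² at 180 days. Neither is a 3-year result.
- Assumptions, not in the documents: b from 1% to 5%; m = 0, then m from −0.5 to +0.5 mm².

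| A | m | b = 1% | b = 5% |
|---|---|---|---|
| +0.32 | 0 | +0.0032 | +0.0160 |
| −0.23 | 0 | −0.0023 | −0.0115 |
| +0.32 | −0.5 | +0.0082 | +0.0410 |
| −0.23 | +0.5 | −0.0073 | −0.0365 |

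**4. Error rate, to show that it depends on an assumed sign.** Take 100:50, a normal approximation and no true ITT difference. SE = √(1/100 + 1/50) = 0.173 SD. If excluded subjects do d SD worse than the rest, the chance of falsely declaring Absorb superior is 1 − Φ(1.96 − bd/0.173).

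- b = 5%, d = 0.5 to 1.5: 0.035 to 0.063, against a nominal 0.025.
- d = 0: 0.025.
- b = 5%, d = −1: 1 − Φ(1.96 + 0.289) = 0.012.

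**The case against.** The strongest reply is that this is a deliberate, pre-specified rule. It appears in two sections, and 7.3.8 distinguishes it from TVR, where subjects are not replaced. Section 10.4.2 names PTE as well as ITT. The Imaging Cohort asks a mechanistic question about device-treated segments, and a lesion holding both devices may not answer it; after acute occlusion the XIENCE may cover the whole scaffold. The population sections are blacked out, and the only SAP supplied covers ABSORB IV (SAP 1.1). The test is secondary and follows only if the TLF test passes.

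Most of this stands as a case for having a mixed-device exclusion somewhere. It does not make the resulting set ITT. The redactions limit certainty, but the visible sections still do not fit together.

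A reader might also infer more than the text supports:

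- **That all Absorb bailouts are dropped.** Absorb-with-Absorb stays in.
- **That replacements must be uncomplicated cases.** They need only lack metallic overlap.
- **That the sample-size sentence in 6.4, "Registered subjects count toward the total sample size in ABSORB III", is a further conflict.** It concerns registration and adds none.

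**Conclusion.** The point holds as a mismatch between the named population and the subjects analysed. On the visible text, the ITT version of the IVUS lumen-area test omits randomised Absorb subjects whose measurements are required, and may use substitutes. It should be corrected, subject to what the blacked-out sections or the ABSORB III SAP may define.

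A reader might infer that the rule favours Absorb or inflates the type I error. The documents support neither. Section 5.2 links scaffold weakening to outward remodelling, so metal could limit late gain. The Cohort A account in 2.1.9 links late loss to premature loss of support, so metal could instead preserve the lumen. The Cohort B fall at 180 days is reported without that attribution. The illustrative shifts run from about −0.037 to +0.041 mm² under assumed bailout rates and lumen changes, and the false-positive chance moves up or down with the assumed sign. No size, direction or error rate is claimed.

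**What to change.** - **ITT analysis of lumen-area change:** include the post-procedure and 3-year IVUS of metal-bailout subjects in their randomised arm, and do not let replacements stand in for them.
- **PTE or a sensitivity analysis:** confine the mixed-device exclusion to these.
- **ABSORB Japan:** handle the pooled subjects by the same rule.
- **Vasomotion, prior TLR and assigned device not received:** call the analysed set a modified, non-ITT population.
- **Reporting:** give the numbers excluded, replaced and not imaged, by arm, with reasons.
- **If an imaging-specific population already exists:** name it in 10.4.2 in place of ITT, and add the inclusive analysis as a sensitivity analysis.

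The cost is wording in 7.3.5, 7.3.8, 10.4.2 and the ABSORB III SAP, plus a check of how ABSORB Japan treats metallic bailout. No new test and no change to the bailout rules is needed. The downside is a slightly larger variance and possibly a less favourable Absorb estimate.

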7.3.8.1 QCA of Target Vessel

- QCA will be performed pre-procedure, post-procedure and at the 3-year follow-up for the imaging study subjects.
- Angiography must be performed per the angiographic core laboratory guidelines.

7.3.8.2 IVUS Pull-back of Target Vessel

- IVUS pullback (20 MHz or 40-45 MHz catheter can be used) is required post-procedure and at 3-year follow-up for the imaging study subjects.
- Pullback of the IVUS catheter should be performed from the distal reference to the guiding catheter, per IVUS core laboratory guidelines.
- If IVUS reveals any findings such that additional PCI is performed, an additional IVUS run must be performed after the last intervention.
- **Caution:** It is important to place the IVUS transducer in the center of the lumen to avoid lifting or disturbing the device struts during pullback.

7.3.8.3 OCT of the Target Vessel

- OCT pullback is required post-procedure and at 3-year follow-up for the imaging study subjects.
- OCT pullback should contain at least one recognizable landmark, usually a major side branch.
- **Caution:** It is important to place the OCT transducer in the center of the lumen to avoid lifting or disturbing the device struts during pullback.

7.3.8.4 Vasomotion Assessment

- At the 3-year follow-up, assessment of vessel movement in response to nitroglycerin infusion will be conducted. Please see the Imaging Guidance Document for the details of this assessment.
- Vasomotion assessment should not be assessed under the following conditions, and those subjects may be replaced for the imaging analysis:

- Target lesion treated with Absorb BVS with metallic stent overlap
 - Target lesion undergoing other PCI procedures prior to 3-year imaging follow-up
 - If target lesion has $\geq 50\%$ stenosis at the time of the 3-year assessment and does not clearly require revascularization, FFR should be conducted to determine if lesion is flow limiting. If the lesion is flow limiting and requires revascularization, vasomotion assessment should not be done.
- Details regarding the angiographic assessment of the vessel and timing of nitroglycerine infusion are further detailed in the Imaging Guidance Document.

7.4 *Post-procedure*

7.4.1 *Post-procedure Information to be Recorded*

The following information needs to be obtained between 12 hours following the index procedure and hospital discharge (in-hospital stay is considered to be a maximum of 7 days following the index procedure).

Between 12 hours post-procedure and discharge

- Date of discharge
- Antiplatelet medications
- Chronic concomitant medications
- Adverse Events, if any

7.4.2 *Post-procedure Laboratory and Clinical Tests*

The following laboratory assessments need to be obtained between post-index procedure and hospital discharge. Hospital discharge cannot occur prior to 16 hours to ensure complete post-procedure cardiac enzyme collection.

IMPORTANT: These tests must be performed whether or not they are considered part of the Investigator's standard of clinical practice.

Post-procedure and discharge

- A 12-lead ECG must be obtained between 30-90 minutes post procedure.
- Both Creatine kinase (CK) and Creatine kinase myocardial-band isoenzyme (CK-MB) must be obtained for ALL registered subjects as it will be used for cardiac assessment of subjects post-index procedure
 - Pre-procedure CK and CK-MB draw*
 - First post-procedure CK and CK-MB draw at 6 to 12 hours post-procedure.

- Second post-procedure CK and CK-MB draw at 18-24 hours post-procedure, or at the time of discharge as long as discharge is at or after 16 hours post-procedure**.
- If either of the post-procedure CK-MB levels are $\geq 3 \times$ ULN, serial CK and CK-MB levels must be drawn until they are falling.

* If the patient has stable coronary artery disease, the pre-procedure level can be obtained during procedure but prior to stent/scaffold deployment. If the patient has a recent acute coronary syndrome, the pre-procedure level must be obtained prior to the procedure and the CKMB shown to be within normal limits prior to the patient being randomized.

** For hospitals required to discharge stable subjects prior to 16 hours, the subject may be discharged but will have to return to the enrolling institution for their second biomarker draw.

CK and CK-MB levels are required at all time points. If troponin is collected at the pre-procedure or post-procedure time points, this should also be documented in the electronic case report forms

7.4.3 Follow-up Antiplatelet Medications

All subjects will be maintained at a minimum of 75 mg of clopidogrel daily or 5 or 10 mg of prasugrel daily (10 mg preferred in most patients) or 90 mg twice daily of ticagrelor for a minimum of 12 months following the procedure. For prasugrel subjects < 60 kg in weight or ≥ 75 years of age, a maintenance dose of 5 mg per day for 12 months is allowable. Patients with prior stroke or TIA should receive clopidogrel or ticagrelor, not prasugrel. All subjects must receive between ≥ 75 to ≤ 100 mg of aspirin daily through 5 years follow-up during the study and should continue to take aspirin indefinitely.

Refer to respective prescribing information for ADP antagonist for further details regarding maintenance dose.

The start of anti-platelet medications, any changes or discontinuation of the medications, as well as the reasons for those change will be documented in the eCRF.

7.4.4 Other Chronic Concomitant Medications

Administration of concomitant medications other than any approved ADP antagonist and aspirin are not required in this protocol/CIP. Subjects may receive other medications as needed per physician's discretion. These concomitant medications must be recorded if the medications are expected to continue for more than 3 months. However, antiplatelet medications must be recorded regardless of duration.

The use and changes for the following classes of chronic concomitant medications, including dosage, frequency and route of administration should be recorded.

- Cardiovascular Medications: Angiotensin converting enzyme inhibitors and angiotensin receptor blockers, renin inhibitor, beta blockers, calcium channel blockers, diuretics, coumadin, other chronic anticoagulants or anti-platelet agents (e.g. rivaroxaban, apixaban, dabigatran, cilostazol), vasodilators, statins, and other lipid lowering agents

- Non-cardiovascular Medications: Systemic anti-inflammatory medications, hormone replacement therapy and diabetic medications

7.5 Clinical and Imaging Follow-up for All Subjects

Clinical follow-up will be performed periodically at the following intervals for all subjects:

- 30 ± 7 days follow-up telephone contact/office visit
- 180 ± 28 days follow-up telephone contact/office visit
- 1 year ± 28 days office visit and ECG³⁵
- 2 years ± 28 days follow-up telephone contact/office visit
- 3 years ± 28 days follow-up telephone contact/office visit
- 4 years ± 28 days follow-up telephone contact/office visit
- 5 years ± 28 days follow-up telephone contact/office visit

Registered subjects must be clinically followed even if no assigned device is implanted. Clinical follow-up visits can also be conducted by a blinded Nurse Practitioner or Physician Assistant that has been trained to the protocol.

For the 2,000 primary analysis subjects of ABSORB III, Patient Reported Outcome follow-up assessments will be conducted as the followings:

- 30 ± 7 days follow-up, in-person, mail, or phone (EQ-5D, SAQ, RDS, GAD-7)
- 1 year ± 28 days office visit (EQ-5D, SAQ, RDS, GAD-7)
- 2 years ± 28 days follow-up, in-person, mail, or phone (EQ-5D, SAQ, RDS, GAD-7)
- 3 years ± 28 days follow-up, in-person, mail, or phone (EQ-5D, SAQ, RDS, GAD-7)
- 5 years ± 28 days follow-up, in-person, mail, or phone (EQ-5D, SAQ)

The questionnaires will be mailed to the subject for completion or can be completed during the phone or office visit. If questionnaires are mailed to the subjects, the subjects must mail the questionnaires back to the clinical site.

³⁵ ECG can be obtained outside of the investigational site but must be reviewed by one of the site investigators and obtained within the protocol visit window. If an investigator suspects that a subject, with a negative ECG, will require a diagnostic angiogram due to possible cardiac symptoms, a functional study must be performed prior to the angiogram to confirm whether the patient has ischemia. This must be done whether or not it is a site standard, due to the use of the ARC definition to adjudicate ischemia driven revascularization.

In addition to the clinical follow-up, imaging follow-up will be performed at the following intervals for the Imaging Cohort:

- Post-procedure: angiography and IVUS (~150 subjects) or angiography and OCT (~50 subjects)
- 3 years \pm 28 days follow-up office visit and ECG: subjects in the Imaging Cohort (n=150) will receive follow-up angiography and IVUS.
- 3 years \pm 28 days follow-up office visit and ECG: subjects in the Imaging Cohort (n=50) will receive follow-up angiography and OCT.

Imaging Cohort subjects are required to undergo only one of the imaging follow-up time-points.

The following information will be collected at each of the time points:

- Any adverse events*, medications, laboratory tests and 12-lead ECGs, if performed;
- Any repeat coronary angiography and results of such, if applicable;
- Details of any subsequent coronary interventions (e.g., repeat PCI or CABG);
- Use and compliance of medications per clinical investigation plan;
- Use and changes in concomitant cardiovascular medications.

* All adverse events must be collected up to and including to the 1 year follow up for all 2250 subjects. Following the 1-year follow-up, it is mandatory to collect information on cardiac adverse events, device related adverse events and on serious adverse events.

